## 10.3.3. Interim Analyses

Safety, PK and pulmonary hemodynamic data will be reviewed after 4 subjects have completed dosing in each cohort prior to dosing at the next level. A linear regression model may be fitted to the (log transformed, if necessary) Change from Baseline at 4h PVR, CO and/or mPAP data from the first three cohorts (Dose Vs baseline adjusted response); and the slope parameter estimated along with the (extrapolated) mean response for the planned 4th dose of 0.8mg/kg. This will be used in addition to safety, PK and other PD data, to aid the team in decision making with regards to additional subject recruitment at an optimum dose level(s).

The RAP will describe the planned interim analyses in greater detail.

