# 5.2. Number of Participants

The total number of participants recruited will be determined through an ongoing review of the safety, tolerability, PK and PD data with a minimum of 4 participants recruited per cohort. There will be 4 cohorts. At the end of each cohort a dose escalation meeting will occur and a decision will be made whether to dose escalate.

Once dose escalation is complete additional participants may be recruited to further evaluate findings at a given dose level. A maximum of 27 participants will complete dosing and critical assessments in this study.

Evaluable participants are defined in Section 10.2.

If participants prematurely discontinue the study, additional replacement participants may be recruited and assigned to the same dose level at the discretion of the Sponsor in consultation with the investigator.

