#### 5.5. Dose Justification

GSK2586881 has been studied in 21 healthy subjects as single, intravenous doses over 30 minutes from 0.1 mg/kg to 1.2 mg/kg, and in repeated daily doses for up to six days of 0.4 mg/kg once a day. In addition, ARDS patients have received four doses of GSK2586881: 0.1 mg/kg, 0.2 mg.kg, 0.4 mg/kg and 0.8 mg/kg over a 24 hour period (n=5) or 0.4 mg/kg BID for 3 days (n=19).

A preliminary population PK model for GSK2586881 has been derived from data obtained in healthy subjects and ARDS patients and showed that the systemic PK profile was adequately described by a two-compartment first order elimination model and that the PK profile was independent of population (healthy subjects or ARDS patients). Decreases in Ang II levels occurred rapidly after GSK2586881 administration with Ang II concentrations maximally or near maximally reduced at the first sampling time of 5 minutes post-dose; consistent with maximal plasma concentrations of GSK2586881. The PK/PD response (the relationship between ACE2 and Ang II) in healthy subjects and ARDS patients appeared to be best described with a single direct Emax model after accounting for differences in baseline Ang II concentrations between healthy subjects and ARDS patients. The observation of no significant delay between GSK2586881 concentration and effect is in line with its mechanism of action as an enzyme on a substrate.

Based on the preliminary population PK/PD model described above, it is predicted that following a single dose of ≥0.2 mg/kg, Ang II concentrations will on average be reduced below participant baseline levels for at least 24 hours post-dose (assuming Ang II levels in PAH participants is consistent with levels reported in ARDS participants in GSK study ACE114622 (GSK Document Number 2014N217963\_00). The 0.8mg/kg dose has been selected to investigate the safety and tolerability dose range for GSK2586881 in this patient population.

In an investigator-sponsored study (NCT01884051) GSK2586881 has been studied in 3 PAH patients as a single, intravenous dose at 0.2 mg/kg, and in 2 patients at 0.4mg/kg. There were no SAEs and no dose limiting toxicities were observed.

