## 10.3.1. Pharmacodynamic and Safety Analyses

Endpoint	Statistical Analysis Methods		
Primary	Descriptive Summaries, Figures and Listings of Change from Baseline PVR, CO and mPAP by planned timepoints.		
	
 
If data permit, linear regression of Dose vs Change from Baseline PVR, CO and/or mPAP at 4 hours (endpoints loge transformed if necessary).
 
		
Secondary	Descriptive Summaries, Figures and Listings.		
	
 
Simple figures (e.g. scatterplots and/or scatterplot matrix plots)     exploring correlation between key PD endpoints (e.g. RAS peptides)     and the Primary endpoints (PVR, CO and mPAP).
 
		
	All safety analyses will be performed on the Safety Population		
Exploratory	Will be described in the RAP. Note that exploratory genetic analyses, should they occur will be detailed in a separate RAP.		

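### Does the optional interim regression lean too heavily on a straight line extrapolated to 0.8 mg/kg?

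*Protocol*

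**What the plan says.** Section 10.3.3 (Interim Analyses) makes the model optional and attaches the log option to the response: "A linear regression model may be fitted to the (log transformed, if necessary) Change from Baseline at 4h PVR, CO and/or mPAP data". The data are those of the first three cohorts and the regressor is named simply as dose. The output is described as "the slope parameter estimated along with the (extrapolated) mean response for the planned" fourth dose, 0.8 mg/kg. On the use of the result it says: "This will be used in addition to safety, PK and other PD data, to aid the team" in deciding on further recruitment at one or more optimum dose levels. The section closes by leaving the detail of the interim analyses to the reporting and analysis plan (RAP).

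Section 10.3.1 lists descriptive summaries, figures and listings first for the primary endpoints, then, if data permit, "linear regression of Dose vs Change from Baseline PVR, CO and/or mPAP at 4 hours".

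Sections 5.2 and 7.2 set at least 4 participants per cohort, allow cohort sizes to vary and allow expansion. Section 5.2 also says: "Once dose escalation is complete additional participants may be recruited to further evaluate findings at a given dose level", and "A maximum of 27 participants will complete dosing and critical assessments in this study".

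Section 5.5 reports one exposure-response shape: the relation of ACE2 concentration to Ang II in healthy subjects and ARDS patients "appeared to be best described with a single direct Emax model".

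**The concern.** The planned doses are exact doublings, yet on the natural reading the regression uses untransformed dose and predicts at twice the highest fitted dose. Such a prediction has a large variance, and if the hemodynamic response saturates it is also too high. Section 5.5 makes saturation thinkable, because the Ang II relation has that form. The stated use is to help choose where extra participants go, and up to 27 - 4 x 4 = 11 participants are not tied to the cohort minimum. If the extrapolated mean drove that choice, chance could send a large part of a small trial to the wrong dose level. The same dose scale appears in the final regression of Section 10.3.1, where the 0.8 mg/kg cohort has a strong pull on the slope.

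**Working it through.** The protocol states no precision, power or SD (Section 10.1 says the sample size has no statistical basis), so there is no figure of its own to reproduce. Results are in units of the residual SD.

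**Precision at the minimum cohort size.** Inputs: doses 0.1, 0.2, 0.4 mg/kg and prediction at x0 = 0.8 (Section 7.2); 4 per cohort, N = 12 (Section 10.3.3). Assume independent errors, constant variance and a true straight line. Variance of the fitted mean = 1/N + (x0 - mean)²/Sxx.

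- mean = 0.7/3 = 0.2333; Sxx = 4 x (0.1333² + 0.0333² + 0.1667²) = 0.18667
- variance = 1/12 + 0.5667²/0.18667 = 1.804; SE = 1.34
- 95% half-width = 2.228 x 1.343 = 2.99 (10 df)
- equivalent observed participants = 1/1.804 = 0.55

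The prediction weights the three cohort means by -1.29, -0.07 and +2.36, so it is close to a magnified difference between the outer two cohorts. Four participants observed at 0.8 mg/kg would give SE 0.50.

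**Other cohort sizes.** Three equal cohorts of 7 give SE 1.02. Cohorts may be unequal: 4/4/10 (18 participants) gives mean 0.2889, Sxx 0.2978, variance 1/18 + 0.5111²/0.2978 = 0.933 and SE 0.97. With 6/4/13 (23 participants, leaving 4 of the 27 for 0.8 mg/kg) the SE is 0.83. The figure of about half a participant therefore belongs to the minimum cohort size.

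**Log dose as the alternative.** Code the doses 0, 1, 2 and predict at 3: Sxx = 4 x 2 = 8, variance = 1/12 + 4/8 = 0.583, SE 0.76, half-width 1.70. The gain comes from a shorter extrapolation on the chosen scale, not from more data, and the smaller SE describes the error only if the response is linear in log dose.

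**Bias at 0.8 mg/kg under assumed shapes.** Each model is fitted to the exact means at 0.1, 0.2 and 0.4 mg/kg, and its prediction is compared with the exact value at 0.8. All shape parameters are assumptions; the protocol gives none for these endpoints.

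| True shape | Straight line | Log dose |
|---|---|---|
| Emax, ED50 0.02 to 0.8 mg/kg | +14% to +38% | -13% to +8% |
| Emax, ED50 3.2 mg/kg | +9% | -26% |
| Proportional to dose | 0% | -33% |
| Sigmoid, Hill 2, ED50 0.8 mg/kg | -11% | -45% |

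Log dose does better in the first row and worse in the other three. Nothing in the protocol says which row applies: the Emax result of Section 5.5 concerns Ang II against concentration, in other populations.

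**Final fit.** With 4 per cohort at all four doses, the squared deviations from the mean dose 0.375 are 0.0756, 0.0306, 0.0006 and 0.1806. The 0.8 mg/kg share is 0.1806/0.2875 = 63%; on log2 dose it is 2.25/5 = 45%. This is the leverage of an observed extreme dose. It is not extrapolation, and in itself it is not bias.

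**Reach of the prediction.** It needs the first three cohorts, so additions made after the first or second review cannot depend on it. Additions after escalation is complete can use observed 0.8 mg/kg data. Its own window lies between the third review and the first 0.8 mg/kg results, so 11 is an upper bound, reached only if no extra participants were added earlier.

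**The case for a change.** The strongest argument for a change is that imprecision holds even if the line is exactly right. If the true mean effect at 0.8 mg/kg were 1 residual SD, the prediction would have the wrong sign with probability Φ(-1/1.343), about 23%, against Φ(-2), about 2%, for four observed participants. Being one input among several does not make such an estimate informative. Both statistical sections name dose and offer a log option only for the endpoints, so the dose scale looks settled rather than left open. Section 10.3.3 also asks for a mean without mentioning an interval, and the remedy would cost only wording.

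The imprecision stands, and untransformed dose is the natural reading. The rest does not amount to a fault. A rule that the extrapolated mean must not decide alone would add nothing to a paragraph that already makes it an aid beside other data. An interval next to the cohort means is good practice, but it is the kind of detail the section leaves to the RAP, which was not available here; nothing in the protocol says the mean will be shown without one. Making log dose the main scale exchanges one unverified assumption for another.

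**Conclusion.** The concern does not hold. The arithmetic is right: at 4 per cohort on untransformed dose the extrapolated mean has SE 1.34 residual SD and is worth 0.55 of one observed participant, assuming a true straight line with constant variance. But the protocol claims no more for it than that. It offers an optional, openly extrapolated estimate as one aid among several in a small exploratory study, and 0.8 mg/kg is itself a planned cohort whose observed data can supersede the prediction. The choice between dose and log dose is a trade-off that cannot be settled from the protocol, because it gives no dose-response shape for PVR, CO or mPAP. The 63% share in the final fit is ordinary leverage from an observed dose. No statement or figure in Sections 10.3.1 or 10.3.3 is wrong, and showing the interval with any prediction can be left to the RAP.

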# 12. APPENDICES

# 12.1. Appendix 1: Abbreviations and Trademarks

# **ABBREVIATIONS**

2D	Two-dimensional
6MW	Six minute walk
ACE2	Angiotensin converting enzyme type 2
AE	Adverse Event
ALT	Alanine aminotransferase (SGPT)
Ang II	Angiotensin II
ARDS	Acute respiratory distress syndrome
AST	Aspartate aminotransferase (SGOT)
aPTT	Activated prothrombin time
$AUC(0-\infty)$	Area under the plasma concentration-time curve
AUC(0-t)	Area under the concentration-time curve from time zero (pre-dose) to last time of quantifiable concentration within a subject across all treatments
BID	Bi-Daily
BMI	Body mass index
BP	Blood pressure
BUN	Blood urea nitrogen
CIOMS	Council for International Organizations of Medical Sciences
Clast	Last observed quantifiable concentration
CL	Plasma clearance
Cmax	Maximum observed plasma concentration
CO	Cardiac output
CONSORT	Consolidated Standards of Reporting Trials
COPD	Chronic Obstructive Pulmonary Disease
CPK	Creatine phosphokinase
CRF	Case Report Form
CRM	Continual reassessment model
CSR	Clinical study report
CV	Cardiovascular
DLT	Dose limiting toxicity
DNA	Deoxyribonucleic acid
ECG	Electrocardiogram
eCRF	Electronic case report form
eGFR	Estimated glomerular-filtration-rate
FDA	Food and Drug Administration
FSH	Follicle Stimulating Hormone
FTIH	First time in humans
GCP	Good Clinical Practice
GFR	Glomerular-filtration-rate
GSK	GlaxoSmithKline

HB	hamoglahin		
	hemoglobin  Hamatitis B. surface antigen		
HBsAg hCG	Hepatitis B surface antigen		
	Human chorionic gonadotropin		
HIPAA	Health Insurance Portability and Accountability		
HIV	Human Immunodeficiency Virus		
HPAH	Heritable PAH		
HPLC	High performance liquid chromatography		
HR	Heart rate		
HRT	Hormone replacement therapy		
IB	Investigator's Brochure		
ICH	International Conference on Harmonization of Technical Requirements		
	for Registration of Pharmaceuticals for Human Use		
ICF	Informed Consent Form		
IEC	Independent Ethics Committee		
IgG	Immunoglobulin G		
IgM	Immunoglobulin M		
IND	Investigational New Drug		
INR	International normalized ratio		
IP	Investigational Product		
IPAH	Idiopathic PAH		
IRB	Institutional Review Board		
IUD	Intrauterine device		
IUS	Intrauterine hormone-releasing system		
IV	Intravenous		
IWRS	Interactive Web Response System		
LDH	Lactate dehydrogenase		
MCH	Mean corpuscular hemoglobin		
MCV	Mean corpuscular volume		
MedDRA	Medical Dictionary for Regulatory Activities		
mPAP	Mean pulmonary arterial pressure		
MSDS	Material Safety Data Sheet		
MTD	Maximal tolerated dose		
NO	Nitric oxide		
NSAIDS	Nonsteroidal anti-inflammatory drugs		
NSVT	Non-sustained ventricular tachycardia		
PAC	Pulmonary arterial catheterization		
PAH	Pulmonary Arterial Hypertension		
PAP	Pulmonary arterial pressure		
PAsat	Pulmonary artery saturation		
PCW	Pulmonary capillary wedge		
PD	Pharmacodynamic		
PDE	Phosphodiesterase		
PDMP	Protocol Deviation Management Plan		
PGx	Pharmacogenetics		
PK	Pharmacokinetic		
PT	Prothrombin time		
1.1	1 TOWN OFFICE WHILE		

DVC	
PVC	Premature Ventricular Complexes
PVR	Pulmonary vascular resistance
QTcB	QT duration corrected for heart rate by Bazett's formula
QTcF	QT duration corrected for heart rate by Fridericia's formula
R&D	Research and development
RAP	Reporting and Analysis Plan
RAS	Renin-Angiotensin System
RBC	Red blood cells
rhACE2	Recombinant human angiotensin converting enzyme type 2
RNA	Ribonucleic acid
SAE	Serious adverse event(s)
SaO 2	Oxygen saturations
SGOT	Serum glutamic-oxaloacetic transaminase
SGPT	Serum glutamic pyruvic transaminase
SOA	Schedule of Activities
SOP	Standard Operating Procedure
SRM	Study Reference Manual
SUSAR	Suspected, Unexpected, Serious Adverse drug Reaction
t½	Terminal phase half-life
tlast	Time of last quantifiable concentration
tmax	Time of occurrence of Cmax
ULN	Upper limit of normal
$V_{\mathrm{D}}$	Volume of distribution
WHO	World Health Organization
WOCBP	Women of Childbearing Potential

# **Trademark Information**

Trademarks of the GlaxoSmithKline group of companies	
NONE	

Trademarks not owned by the GlaxoSmithKline group of companies WinNonlin

## 12.2. Appendix 2: Clinical Laboratory Tests

- The tests detailed in Table 1 will be performed by the central laboratory.
- If a local sample is required, it is important that the sample for central analysis is obtained at the same time.
- Protocol-specific requirements for inclusion or exclusion of participants are detailed in Section 6 of the protocol.
- Additional tests may be performed at any time during the study as determined necessary by the investigator or required by local regulations.

 Table 1
 Protocol-Required Safety Laboratory Assessments

Laboratory Assessments	Parameters			
Hematology	Platelet Count RBC Count Hemoglobin Hematocrit		RBC Indices: MCV MCH %Reticulocytes	WBC count with Differential: Neutrophils Lymphocytes Monocytes Eosinophils Basophils
Clinical Chemistry 	BUN	Potassium	Aspartate Aminotransferase (AST)/ Serum Glutamic- Oxaloacetic Transaminase (SGOT)	Total and direct bilirubin
	Creatinine	Sodium	Alanine Aminotransferase (ALT)/ Serum Glutamic- Pyruvic Transaminase (SGPT)	Total Protein
	Glucose	Calcium	Alkaline phosphatase	International normalized ratio (INR) Activated Prothrombin time (PT) aPTT
Routine Urinalysis	
 
Specific gravity
 
pH, glucose, protein, blood, ketones, bilirubin, Microscopic examination (only if blood or protein is abnormal)
 
			
Other Screening Tests	
 
Follicle-stimulating hormone and estradiol (as needed in women of non-childbearing potential only)
 
Serum or urine human chorionic gonadotropin (hCG) pregnancy test (as needed for women of childbearing potential)
 
			

Laboratory Assessments	Parameters		
	Serology (HIV antibody, hepatitis B surface antigen [HBsAg], hepatitis C RNA and hepatitis C virus antibody)		

#### NOTES:

- Details of liver chemistry stopping criteria and required actions and follow-up assessments after liver stopping or monitoring event are given in Section 8.1 and Appendix 7. All events of ALT ≥3 × upper limit of normal (ULN) and bilirubin ≥2 × ULN (>35% direct bilirubin) or ALT ≥3 × ULN and international normalized ratio (INR) >1.5, if INR measured, which may indicate severe liver injury (possible Hy's Law), must be reported as an SAE (excluding studies of hepatic impairment or cirrhosis).
- 2. Local urine testing will be standard for the protocol unless serum testing is required by local regulation or IRB/IEC.

## 12.3. Appendix 3: Study Governance Considerations

## **Regulatory and Ethical Considerations**

- This study will be conducted in accordance with the protocol and with:
  - Consensus ethical principles derived from international guidelines including the Declaration of Helsinki and Council for International Organizations of Medical Sciences (CIOMS) International Ethical Guidelines
  - Applicable ICH Good Clinical Practice (GCP) Guidelines
  - Applicable laws and regulations
- The protocol, protocol amendments, ICF, Investigator Brochure, and other relevant documents (e.g., advertisements) must be submitted to an IRB/IEC by the investigator and reviewed and approved by the IRB/IEC before the study is initiated.
- Any amendments to the protocol will require IEC/IRB approval before implementation of changes made to the study design, except for changes necessary to eliminate an immediate hazard to study participants.
- The investigator will be responsible for the following:
  - Providing written summaries of the status of the study to the IRB/IEC annually or more frequently in accordance with the requirements, policies, and procedures established by the IRB/IEC
  - Notifying the IRB/IEC of SAE or other significant safety findings as required by IRB/IEC procedures
  - Providing oversight of the conduct of the study at the site and adherence to requirements of 21 CFR, ICH guidelines, the IRB/IEC, European regulation 536/2014 for clinical studies (if applicable), and all other applicable local regulations

#### **Financial Disclosure**

Investigators and sub-investigators will provide the sponsor with sufficient, accurate financial information as requested to allow the sponsor to submit complete and accurate financial certification or disclosure statements to the appropriate regulatory authorities. Investigators are responsible for providing information on financial interests during the course of the study and for 1 year after completion of the study.

#### **Informed Consent Process**

• The investigator or his/her representative will explain the nature of the study to the participant or his/her legally authorized representative and answer all questions regarding the study.

- Participants must be informed that their participation is voluntary. Participants
  or their legally authorized representative will be required to sign a statement of
  informed consent that meets the requirements of 21 CFR 50, local regulations,
  ICH guidelines, Health Insurance Portability and Accountability Act (HIPAA)
  requirements, where applicable, and the IRB/IEC or study center.
- The medical record must include a statement that written informed consent was obtained before the participant was enrolled in the study and the date the written consent was obtained. The authorized person obtaining the informed consent must also sign the ICF.
- Participants must be re-consented to the most current version of the ICF(s) during their participation in the study.
- A copy of the ICF(s) must be provided to the participant or the participant's legally authorized representative.
- Participants who are rescreened are required to sign a new ICF.

#### **Data Protection**

- Participants will be assigned a unique identifier by the sponsor. Any participant records or datasets that are transferred to the sponsor will contain the identifier only; participant names or any information which would make the participant identifiable will not be transferred.
- The participant must be informed that his/her personal study-related data will be used by the sponsor in accordance with local data protection law. The level of disclosure must also be explained to the participant.
- The participant must be informed that his/her medical records may be examined by Clinical Quality Assurance auditors or other authorized personnel appointed by the sponsor, by appropriate IRB/IEC members, and by inspectors from regulatory authorities.

## **Publication Policy**

- The results of this study may be published or presented at scientific meetings. If this is foreseen, the investigator agrees to submit all manuscripts or abstracts to the sponsor before submission. This allows the sponsor to protect proprietary information and to provide comments.
- The sponsor will comply with the requirements for publication of study results.
   In accordance with standard editorial and ethical practice, the sponsor will generally support publication of multicenter studies only in their entirety and not as individual site data. In this case, a coordinating investigator will be designated by mutual agreement.
- Authorship will be determined by mutual agreement and in line with International Committee of Medical Journal Editors authorship requirements.

## **Dissemination of Clinical Study Data**

 This study will be registered and study information from this protocol will be posted on publicly available clinical trial registers before enrolment of study participants begins.

CONFIDENTIAL

- The results summary of this study will be posted to the GSK Clinical Study Register and other publicly available clinical trial registers within 8 months of the primary study completion date.
- A manuscript reporting the study results will be submitted to a peer reviewed journal within 18 months of the last participant's last visit.

## **Data Quality Assurance**

- All participant data relating to the study will be recorded on printed or electronic CRF unless transmitted to the sponsor or designee electronically (eg, laboratory data). The investigator is responsible for verifying that data entries are accurate and correct by physically or electronically signing the CRF.
- The investigator must maintain accurate documentation (source data) that supports the information entered in the CRF.
- The investigator must permit study-related monitoring, audits, IRB/IEC review, and regulatory agency inspections and provide direct access to source data documents.
- The sponsor or designee is responsible for the data management of this study including quality checking of the data.
- Study monitors will perform ongoing source data verification to confirm that
  data entered into the CRF by authorized site personnel are accurate, complete,
  and verifiable from source documents; that the safety and rights of participants
  are being protected; and that the study is being conducted in accordance with the
  currently approved protocol and any other study agreements, ICH GCP, and all
  applicable regulatory requirements.
- Records and documents, including signed ICF, pertaining to the conduct of this
  study must be retained by the investigator for 25 years after study completion
  unless local regulations or institutional policies require a longer retention period.
  No records may be destroyed during the retention period without the written
  approval of the sponsor. No records may be transferred to another location or
  party without written notification to the sponsor.

